Overall, most TEAEs have been mild or moderate in severity. Eight (8) of the 83 (9.6%) subjects who received SEL-212 experienced a total of 14 severe TEAEs. Four (4) subjects experienced a single severe TEAE including anemia, gout, rotator cuff syndrome, and deep vein thrombosis (DVT); 2 subjects experienced 2 severe TEAEs including gastrointestinal haemorrhage and gout; and pulmonary embolism and DVT; and 2 subjects experienced 3 severe TEAEs including: arthralgia, joint swelling, and ligament pain; and presyncope and 2 gout attacks. In addition, 2 subjects who received SEL-212 each experienced a life-threatening TEAE, both anaphylactic reactions.

A total of 6 of the 86 (7.0%) subjects who received KRYSTEXXA experienced a total of 6 severe TEAEs. Subjects experienced a single severe TEAE including: 2 gout, an anaphylactic reaction, drug hypersensitivity, gastroenteritis, and an infusion-related reaction. In addition, 2 subjects who received KRYSTEXXA each experienced a life-threatening TEAE of cerebrovascular accident and hypertensive emergency, respectively. There have been no concerning trends in laboratory values, vital signs, or physical examination findings (data not shown).

Twelve (12) of the 169 (7.1%) subjects enrolled have experienced a total of 14 SAEs. Six (6) of the 83 (7.2%) subjects who received SEL-212 experienced a total of 7 SAEs and 6 of the 86 (7.0%) subjects who received KRYSTEXXA experienced a total of 7 SAEs. Two (2) of the SEL-212 SAEs were considered related or possibly related to SEL-212 and 3 of the KRYSTEXXA SAEs were considered related or possibly related to KRYSTEXXA by the investigator.

No deaths have been reported during the study.

In summary, the safety profile of SEL-212 in the ongoing Phase 2 clinical trial has not demonstrated any unexpected TEAEs. In the dose ranging Phase 2 Study SEL-212/201, in general, TEAEs were most frequently observed after the first treatment cycle and diminished with successive treatment cycles. Therefore, the potential risk of TEAEs did not appear to increase with repeated exposure to SEL-212.

Cohorts 7, 11, 13, and 17 from Phase 2 Study SEL-212/201 represent the dose regimens that will be evaluated in the Phase 3 program; and the dose administered in the Phase 2 study SEL-212/202 (SEL-

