12.2.2.3 Adverse Event Intensity/Severity Grading

AEs will be classified according to the Rheumatology Common Toxicity Criteria, version 2.0 ([Woodworth 2007](#)).

- Grade 1 (mild): AE that is usually transient of short duration; or involves mild or minor symptoms which are of marginal clinical relevance; or is asymptomatic consisting of clinical or diagnostic observations alone; no intervention or only minimal treatment with non-prescription intervention was required. The event does not generally interfere with usual activities of daily living.
- Grade 2 (moderate): AE that is usually alleviated with additional specific therapeutic intervention. The event interferes with usual activities of daily living (e.g., shopping, laundry,

transportation, or ability to conduct finances), causing discomfort but poses no significant or permanent risk or harm to the patient.

- Grade 3 (severe): AE that is medically significant/important but not life-threatening; may require brief hospitalization to prevent the event from worsening; interrupts usual activities of daily living, or significantly affects clinical status, or may require intensive therapeutic intervention.
- Grade 4 (life-threatening): An AE, and/or its immediate sequelae, which is associated with an imminent risk of death or which is associated with physical or mental disabilities that affect or limit the ability of a person to perform activities of daily living (eating, ambulation, toileting, etc.); disability may be persistent or result in significant disability, incapacity or limitation of self-care activities.

For an assessment of anaphylaxis, the clinical criteria for the diagnosis of anaphylaxis will be based on the NIAID/FAAN Symposium criteria ([Sampson 2006](#)).

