13.5.2 Adverse Events / Adverse Drug Reactions

All AEs will be coded and grouped into Preferred Terms (PT) by System Organ Class (SOC), using the most recent MedDRA Version. All AEs will be summarized by SOC and PT.

Summaries by each treatment group for the whole study (i.e., double-blind treatment phase and double-blind extension phase) and for the double-blind treatment phase will be provided on the Safety Set overall and by SOC and PT with the number and percentage of patients reporting TEAEs, serious TEAEs, treatment-related TEAEs, AEs of special interest (AESIs), infusion reactions (this is a study drug-related AE that occurs within 24 hours after initiation of study drug infusion), TEAEs leading to withdrawal and TEAEs leading to death. Additional analysis will be performed on a subset of infusion reactions (this is a study drug-related AE that occurs within 1 hour after completion of study drug infusion) that fulfil the criteria of an Allergic Reaction/Hypersensitivity according to the Rheumatology Common Toxicity Criteria, version 2.0. In the overall summary, additionally, the number and percentage of patients with at least one severe TEAE, with at least one moderate TEAE but no severe TEAE and with only mild TEAEs will be provided. Similar summaries will be produced for the subset of patients continued into the double-blind extension phase (i.e., on the EPS) considering the whole study but also separately for each treatment phase.

The number and percentage of patients with TEAEs / serious TEAEs / treatment-related TEAEs / TEAEs of special interest and TEAEs leading to withdrawal will be summarized by SOC and PT for each treatment group and overall for the whole study and for the double-blind treatment phase on the Safety Set. Similar summaries will be produced for the subset of patients continued into the double-blind extension phase (i.e., on the EPS) considering the whole study but, also separately for each treatment phase.

Event rates by treatment group and overall will be provided for patients with at least one related TEAE, at least one SAE, and at least one TEAE of special interest. Additionally, the rate difference with 95% confidence interval comparing each SEL-212 treatment group to placebo as well as comparing the integrated SEL-212 arms to placebo will be provided.

TEAEs will also be summarized by maximum intensity and relationship to study drug.

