Summary table of actual values and change from baseline will be provided for all subscales of HAQ-DI, for all subscales of SF-36, the two component scores of SF-36, and the PGA, by period and treatment group. Pairwise comparison of each SEL-212 treatment group versus placebo will be performed using MMRM with the change from baseline in the respective health assessment score as dependent variable and treatment, period, treatment by period interaction, randomization stratum, and baseline value of the respective health assessment as fixed effects. The LSMean difference between each SEL-212 and placebo treatments groups will be presented for TP6, along with its 95% confidence interval, and 2-sided p-values.

HAQ-DI subscales and SF-36 subscales and component scores are described in Sections [9.3.2.7](#) and [9.3.2.3](#) of this SAP, respectively. The PGA will be administered to assess the severity of the patient's disease on a scale from 0 (patient feels "very well") to 100 (patient feels "very poor"). Lower scores indicate less severe disease.

- Percentage of Patients with Gout Flares:

Frequency table of the number and percentage of patients reporting at least one gout flare in the study until end of Month 6, in the first 3 months, and the next 3 months will be summarized by treatment group on the ITT population.

This document is confidential.

The number and percentage of patients with at least one life-threatening / at least one severe but no life-threatening / at least one moderate but no severe or life-threatening / only mild gout flares will be presented for each treatment group for all 6 months, but also per 3-month period (first 3 months and next 3 months) on the ITT population.

The percentage of patients with gout flares will be compared between each SEL-212 treatment group versus placebo on the ITT population using the MH estimate and test for common risk difference considering the randomization stratum of tophus presence (yes/no). This analysis will be performed separately for the whole treatment period of 6 months and for the first 3 months after start of study treatment. 95% confidence intervals for treatment differences in proportions between each SEL-212 treatment group and placebo will be computed.

- Change from Baseline to Day 28 of TP6 in number of swollen joints:

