### **10.3. Adverse Events / Adverse Drug Reactions**

All adverse events (AEs) will be coded using the most recent MedDRA Version. All AEs will be summarized by system organ class (SOC) and preferred term (PT) for each treatment group, for overall SEL-212 and in total for the whole study, but also for the double-blind treatment phase and the double-blind extension phase separately. A treatment-emergent AE (TEAE) is an AE that starts or worsens at any time after

This document is confidential.

initiation of study drug on Day 0 of Treatment Period 1 until the End of Study Visit (30 days after completion of the last dose of study drug). TEAEs will be further classified as treatment-emergent for the double-blind treatment phase (these are all AEs which start prior to the first dose in the extension phase) and as treatment-emergent for the double-blind extension phase (these are all AEs which start after the first dose in the extension phase or increase in intensity after start of study drug in the extension phase). Additional analysis will be performed on a subset of infusion reactions (this is a study drug-related AE that occurs within 1 hour after completion of study drug infusion) that fulfil the criteria of an Allergic Reaction/Hypersensitivity according to the Rheumatology Common Toxicity Criteria, version 2.0.

Following AEs are considered as AEs of special interest (AESIs): gout flares, infections, malignancies, viral infections, interstitial lung disease, stomatitis, infusion-related reactions including anaphylaxis, thrombosis (e.g., deep venous thrombosis, pulmonary embolism), and the following laboratory tests, if deemed clinically significant by the PI: hyperlipidemia, worsening of renal function tests, proteinuria, and leukopenia.

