An overall summary will be provided of the number and percentage of patients reporting AEs, TEAEs, treatment-related (possibly related and related) TEAEs, serious TEAEs, treatment-related serious TEAEs, AESIs, infusion reactions (this is a study drug-related AE that occurs within 24 hours after initiation of study drug infusion), infusion reactions (this is a study drug-related AE that occurs within 1 hour after completion of study drug infusion) that fulfil the criteria of an Allergic Reaction/Hypersensitivity according to the Rheumatology Common Toxicity Criteria, version 2.0. Any gout flare which occurs within 24 hours after initiation of study drug infusion will be listed as a gout flare and not as an infusion reaction. TEAEs leading to study drug withdrawal and TEAEs leading to death. In the overall summary, additionally, the number and percentage of patients with at least one severe TEAE, with at least one moderate TEAE but no severe TEAE and with only mild TEAEs will be provided. The overall summary will be provided for all AEs in the study and for the AEs in the double-blind treatment phase on SS. Additionally, the overall summary will be provided for the whole study and for each period on EPS.

The number and percentage of patients with TEAEs / treatment-related TEAEs / serious TEAEs / AESIs / TEAEs leading to study drug withdrawal/ will be summarized by SOC and PT for each treatment group. TEAEs will also be summarized by SOC and PT for maximum intensity and maximum causality for each treatment group. All defined summaries will be provided for all TEAEs in the study and for the TEAEs in the double-blind treatment phase on SS. Additionally above defined summaries will be provided on the EPS for the whole study and for each period.

Exposure-adjusted event rates based on i) patients and also based on ii) events by treatment group, overall SEL-212 and total will be provided for patients with at least one related TEAE, at least one SAE, at least one TEAE of special interest and also for specific TEAEs of special interest. For SAEs and AESIs that occur in  $\geq 2\%$  of individuals, as well as the most common TEAEs, the rate difference of exposure-adjusted event rates between the two treatment groups together with the 95% confidence interval will be provided; this will also be presented for the two treatment groups combined vs. placebo.

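### The severity lines of the adverse-event overview have no tier for Grade 4 (life-threatening) events

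*SAP*

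**What the plan says.** **Overview.** SAP 10.3 plans, alongside the counts of patients with TEAEs, serious TEAEs, AESIs and so on, three severity lines: patients "with at least one severe TEAE, with at least one moderate TEAE but no severe TEAE and with only mild TEAEs will be provided". Protocol 13.5.2 has the same three: "with at least one severe TEAE, with at least one moderate TEAE but no severe TEAE and with only mild TEAEs".

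**Grading.** Protocol 12.2.2.3 uses four grades. The third is "Grade 3 (severe): AE that is medically significant/important but not life-threatening". The fourth is separate: "Grade 4 (life-threatening): An AE, and/or its immediate sequelae, which is associated with an imminent risk of death".

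**Gout flares.** For flare severity, SAP 9.3.3 uses four tiers: "at least one life-threatening / at least one severe but no life-threatening / at least one moderate but no severe or life-threatening", followed by only mild.

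**Earlier experience.** Protocol 7.6.3.2.2 reports severe TEAEs in 8 of 83 SEL-212 patients in study 202 and then adds: "In addition, 2 subjects who received SEL-212 each experienced a life-threatening TEAE, both anaphylactic reactions".

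**Hypersensitivity subset.** SAP 10.3 and Protocol 13.5.2 single out infusion reactions that meet the toxicity criteria for allergic reaction or hypersensitivity. For this subset an infusion reaction is described as follows: "this is a study drug-related AE that occurs within 1 hour after completion of study drug infusion". The general infusion-reaction row runs for 24 hours from the start of infusion.

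**The concern.** The three lines read as a worst-grade classification of every patient with a TEAE. They are not one, because the highest grade is missing. Under the protocol's own definition a Grade 4 event is not severe, so it cannot put a patient on the severe line. Unless the patient also has a Grade 3 event, placement depends on the lesser events.

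The overview is the table most readers will use to judge severity, and infusion reactions including anaphylaxis are a named AESI. A table in which a patient with life-threatening anaphylaxis can be counted as moderate, or not at all, does not do what its labels say.

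The hypersensitivity subset raises a related but lesser question. Its window is anchored at completion of the infusion, and the text does not say whether reactions during the infusion count.

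**Working it through.** **1. The plan's own severity figure.** In study 202 the SEL-212 arm had 8 patients with severe TEAEs: 4 with one event, 2 with two and 2 with three. Events: 4×1 + 2×2 + 2×3 = 14, as stated. Patients: 8/83 = 9.6%, as stated. The two life-threatening cases are reported in addition. If they do not overlap with the eight, severe-or-worse is 10/83 = 12.0%. So the protocol's own reporting keeps Grade 4 outside severe.

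**2. The three tiers applied literally.** A patient with at least one TEAE has one of 2⁴ − 1 = 15 possible sets of grades. Eight contain Grade 4:

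| Grades present | Tier under the current text |
|---|---|
| {3,4}, {1,3,4}, {2,3,4}, {1,2,3,4} | severe, only because a Grade 3 is present |
| {2,4}, {1,2,4} | moderate but no severe |
| {4}, {1,4} | none |

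The seven sets without Grade 4 are all placed correctly. With a life-threatening tier on top, all eight Grade 4 sets go there. These are counts of patterns, not probabilities.

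**3. How many Grade 4 patients to expect.** Input: 2/83 = 2.4%, exact 95% CI 0.29% to 8.43%. Assumption: this rate holds for all 80 SEL-212 patients (40 + 40).

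- Expected number: 80 × 2/83 = 1.9.
- Range from the interval: 80 × 0.0029 = 0.2 to 80 × 0.0843 = 6.7.
- Chance of at least one: 1 − (1 − 2/83)^80 = 0.86.

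The last figure is the chance of any Grade 4 patient, not of a misfiled one. Misfiling requires the absence of a Grade 3 event, and the documents do not give the joint distribution of grades within patients.

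**4. The hypersensitivity window.** By Protocol Appendix B the second infusion ends at about 3.5 h, and Protocol 12.2.1.5 has patients observed to about 4.5 h from the start. If the window opens at completion, it covers 1/4.5 = 22% of that time and none of the infusion itself. This is a share of clock time, not of reactions. Protocol 10.7 has the infusion discontinued when a Grade 3 or 4 reaction occurs during it, and Protocol 12.2.2.5 records a completed dose and a terminated infusion as different actions. A terminated infusion therefore has no completion from which to measure the hour.

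**The case against.** The strongest reply is that nothing is lost. Life-threatening is a criterion for an SAE (Protocol 12.2.1.2), so these patients are counted among serious TEAEs in the same overview. Anaphylaxis is an AESI. A drug-related reaction within 24 hours of the start of infusion has its own row, and so do TEAEs leading to study drug withdrawal. The SOC/PT table by maximum intensity shows Grade 4 where it occurs. All of this stands, and it confines the error to the three severity lines.

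Second, misfiling as moderate needs a particular combination: Grade 4 and Grade 2 without Grade 3. Patients in no tier could be noticed because the tiers would not add up to the TEAE count. Where the documents pool flare severities (Protocol 13.4.2, SAP 9.3.5), they put life-threatening with severe, so a programmer might do the same here. That is plausible, but the overview text does not say so, and a patient filed as moderate leaves no gap in the total.

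Third, a reader might infer that the error falls on the SEL-212 arms and biases the comparison with placebo. The documents do not support that for the severity lines, which cover all TEAEs. In study 202 the comparator arm also had two patients with life-threatening TEAEs, a cerebrovascular accident and a hypertensive emergency, and neither is an infusion reaction. The lower infusion-reaction risk claimed in Protocol 7.7 is relative to available therapy, so it is not a claim about this placebo table.

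Fourth, a reader might infer that the hypersensitivity subset omits every reaction that stops an infusion. That rests on one reading. The text calls it a subset of infusion reactions, which Protocol 12.2.1.5 counts from the start of infusion, so one hour after completion may be meant as the outer limit. The opposite reading is also available, because the 24-hour definition opens at its own anchor. The phrase is ambiguous, which falls short of a shown omission.

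**Conclusion.** The missing Grade 4 tier is a real defect in SAP 10.3 and Protocol 13.5.2. On the literal rule, a patient with a Grade 4 TEAE and no Grade 3 TEAE is shown as moderate or in no tier, in whichever arm the patient is. The conclusion rests on the protocol's grade definitions and on the SAP's own four-tier usage for flares.

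About 2 of 80 SEL-212 patients (0.2 to 6.7) would have a life-threatening TEAE if the study 202 rate applied. That rate comes from an interim cutoff of an open-label study that used only the higher dose, while half of the 80 receive the lower dose. The number misfiled cannot be estimated, and the 86% in the working must not be read as that number.

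The effect is limited to three descriptive lines. No confirmatory analysis is touched, no event disappears from the report, and bias against placebo is not shown. The hypersensitivity window is a secondary matter of clarification.

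**What to change.** In SAP 10.3 and Protocol 13.5.2, replace the three severity lines with the tiers of SAP 9.3.3, applied to TEAEs: "at least one life-threatening / at least one severe but no life-threatening / at least one moderate but no severe or life-threatening", and only mild. State that fatal TEAEs count in the top tier as well as in the existing death row. This sentence is an addition, because SAP 9.3.3 has no fatal tier and the grading scale stops at Grade 4.

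For the hypersensitivity subset, define the window in both documents as running from the start of the first component until one hour after the end of the last component given, whether or not the infusion was completed.

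Both changes use data already collected. The cost is a wording change and minor reprogramming, best settled before unblinding. The downside is a possibly less favourable table.

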13. STATISTICS

Details of the statistical methods outlined in the protocol for this study, including the hierarchical ordering of the secondary endpoints, will be documented in a Statistical Analysis Plan (SAP), which will be finalized prior to database lock. The SAP may add additional exploratory analyses; modifications to the planned analyses will be identified as such in the final SAP.

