#### **9.3.2.8. Gout Flare Incidence During Treatment Periods 1-6**

The gout flare incidence is defined as the total number of gout flares a patient experiences in respective time period divided by the length of observation of the patient in this time period. Both estimands, as well as the estimands where the ITT is replaced by the mITT, all randomized and PP sets, for this key secondary efficacy will be tested between each SEL-212 treatment group versus placebo using ANOVA model with incidence of gout flares as dependent variable and treatment and randomization stratum as fixed effect variables. Missing values of gout flare incidence by TP6-Day 28 will be multiple imputed by using the RPMM method considering tophus status at baseline and treatment group. The LSMean difference between each SEL-212 and placebo treatments groups will be provided along with its 97.5% confidence interval, and 2-sided p-values.

In a supportive analysis, for each defined estimand the comparison between each SEL-212 treatment group and placebo will be performed using MMRM with the dependent variable 'incidence of gout flares in the study (TP1-6)' and treatment, 3-month period (months 1-3 versus months 4-6), treatment-by-3-month period interaction and randomization stratum as fixed effects. The LSMean difference between each SEL-212 and placebo treatment groups will be presented for each 3-month period, along with its 97.5% confidence interval, and 2-sided p-values.

In a further supportive analysis, the total number of gout flares by TP6-Day 28 will be analyzed. Missing values of total number of gout flares by TP6-Day 28 will be multiple imputed by using the RPMM method considering tophus status at baseline and treatment group. The total number of gout flares will be analyzed using an ANOVA with treatment and randomization stratum as fixed effects.

A summary table of the incidence of gout flares during the study and stratified by 3 months period (month 1-3 and month 4-6 after start of study treatment) will be provided by treatment group on the ITT, mITT, all randomized and PP populations. Summary tables of the total number of gout flares during the study will be provided by treatment group and overall and additionally stratified by severity on the ITT, mITT, all randomized and PP populations. Summary tables of the number of gout flares during the first 3 months

This document is confidential.

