### **9.3.3. Additional Secondary Efficacy Endpoints and Analyses**

- Percentage of patients who achieve and maintain reduction of sUA < 6 mg/dL for 100% of the time during TP6:

A frequency table of number and percentage of patients who achieve and maintain reduction of sUA < 6 mg/dL for 100% of the time during TP6 will be provided on the ITT population. Each SEL-212 treatment group will be compared versus placebo using the MH estimate and test for common risk difference considering the randomization stratum of tophus presence (yes/no) on the ITT population. In addition, 95% confidence intervals for treatment differences between each SEL-212 treatment group and placebo will be computed.

- Number with pre-dose sUA values < 6 mg/dL during TPs 2-6 for each patient:

A summary table of the mean number of TPs with pre-dose sUA values < 6 mg/dL during TP2 to TP6 will be provided by treatment group on the ITT population. Each SEL-212 treatment group will be compared versus placebo using ANCOVA model with the number of pre-dose values < 6 mg/dL during TPs 2-6 for each patient as dependent variable and treatment group as independent fixed effect variable. 95% confidence intervals for treatment differences between each SEL-212 treatment group and placebo will be presented.

- Anti-pegadricase and anti-uricase antibody formation and levels, pre-treatment for each treatment period in the SEL-212 active treatment arms during Treatment Periods 1-6:

Summary table of pre-treatment values of each variable will be provided by treatment period and by SEL-212 treatment group on the ITT population.

A descriptive summary table of D21 anti-pegadricase and anti-uricase antibody titers, D21 uricase activity values and D21 SUA values at each treatment period, stratified by treatment arm and whether or not the D21 SUA was above or less than or equal to the stopping rule level for that TP (i.e.  $\leq 1$  mg/dL in TP1 and  $\leq 6$  mg/dL in TPs 2-6).

This document is confidential.

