## **12. Deviation from Analyses Planned in Protocol**

The key secondary endpoints for gout flare will be analyzed by ANOVA instead of ANCOVA as specified in the protocol, as adjustment for baseline is not possible given gout flare incidence is not assessed at baseline.

This document is confidential.

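### As worded, SAP 10.3 gives safety rate differences for SEL-212A vs SEL-212B and for pooled SEL-212 vs placebo, and omits the dose-vs-placebo differences in Protocol 13.5.2

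*SAP*

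**What the plan says.** Protocol 13.5.2 plans event rates by treatment group for patients with at least one related TEAE, at least one SAE and at least one AESI. To these it adds "the rate difference with 95% confidence interval comparing each SEL-212 treatment group to placebo as well as comparing the integrated SEL-212 arms to placebo". The Safety Analyses part of the synopsis says the same.

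SAP 10.3 plans exposure-adjusted rates by treatment group, for SEL-212 overall and in total. These cover the same three patient categories and also specific AESIs. For SAEs and AESIs reaching a 2% threshold, and for the most common TEAEs, it then says the "rate difference of exposure-adjusted event rates between the two treatment groups together with the 95% confidence interval will be provided", and continues: "this will also be presented for the two treatment groups combined vs. placebo".

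On changes, Protocol Section 13 says that "modifications to the planned analyses will be identified as such in the final SAP". SAP Section 12 contains one entry: "The key secondary endpoints for gout flare will be analyzed by ANOVA instead of ANCOVA as specified in the protocol". It does not mention safety.

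**The concern.** The trial has three arms, and the SAP sentence does not name placebo in its first contrast. A programmer who follows it would produce SEL-212A against SEL-212B and pooled SEL-212 against placebo. Neither is a dose-specific comparison with placebo.

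That comparison matters here because the two SEL-212 arms differ only in the SEL-110.36 (rapamycin nanoparticle) dose, 0.1 or 0.15 mg/kg. The AESI list includes stomatitis, leukopenia and hyperlipidemia. Protocol 7.6.3.2.1 discusses stomatitis, leukopenia and hypertriglyceridemia as events of interest for rapamycin. Whether each dose shows an excess over placebo is what the Protocol's contrasts were set up to estimate.

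**Working it through.** The documents give no figure to reproduce, so the check is a comparison of text.

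**1. Which groups the SAP phrase means.** The preceding sentence of SAP 10.3 uses treatment group for any of the three arms. The rate-difference sentence then picks out two of them. Its second clause pools those two and compares them with placebo, so placebo is not one of the two. They are SEL-212A and SEL-212B. The first clause uses the same phrase in the same sentence, so as written its contrast is A vs B.

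**2. Contrasts side by side** (95% intervals in both documents, so the level is not in dispute).

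| Contrast | Protocol 13.5.2 and synopsis | SAP 10.3 as written |
|---|---|---|
| SEL-212A vs placebo | yes | no |
| SEL-212B vs placebo | yes | no |
| SEL-212 combined vs placebo | yes | yes |
| SEL-212A vs SEL-212B | no | yes |

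One of the three required contrasts is kept, two are missing and one is added.

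**3. Whether another section supplies them.** SAP 10.1 to 10.7 contain no other adverse-event difference of each dose against placebo. Where the SAP intends that contrast, it names it. Section 9.3.3 says "95% confidence intervals for treatment differences between each SEL-212 treatment group and placebo will be computed", and Section 9.3.2.8 says "The LSMean difference between each SEL-212 and placebo treatments groups will be provided along with its 97.5% confidence interval". Gout flare, which is also an AESI, is therefore covered through Treatment Period 6. The other events are not.

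**4. Event categories.** The Protocol attaches its differences to three patient-level categories: at least one related TEAE, at least one SAE, at least one AESI. The SAP attaches its differences to SAEs and AESIs at or above 2% and to the most common TEAEs. A difference for related TEAEs is no longer named. Correcting the arms alone would not fully restore Protocol 13.5.2.

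**5. Declared changes.** Safety changes listed in SAP Section 12: none.

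**6. What the two literal outputs can show.** Let r be an arm's event rate and E its exposure, with w_A = E_A/(E_A + E_B) and w_B = 1 − w_A. The pooled rate is w_A·r_A + w_B·r_B, so

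pooled − placebo = w_A(r_A − r_P) + w_B(r_B − r_P).

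If the arms have equal exposure, w_A = w_B = 1/2, and an excess confined to one dose appears at half its size. The A vs B difference contains no placebo term.

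**The case against.** The strongest reply is that the words *vs placebo* were simply left out of the first clause. The SAP sentence has the same two-part structure as the Protocol's: the individual comparisons, then the combined one. The Protocol nowhere asks for A vs B. An empty Section 12 is also what one would expect if no change was intended. As an account of intent this is plausible, and it stands to that extent: the documents do not show a decision to change the analysis.

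It does not repair the sentence. SAP 2.1 makes the CRO responsible for producing the tables, and the sentence it would work from names a different contrast. If no change was meant, the wording is an error. If one was meant, it is undeclared.

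It is also fair to say that these are descriptive summaries. SAP 10.3 still gives numbers and percentages by arm, and exposure-adjusted rates by arm for the three patient categories and for specific AESIs. Point differences for those could be subtracted by hand. Gout flare has its own comparison in Section 9.3.3: "The percentage of patients with gout flares will be compared between each SEL-212 treatment group versus placebo on the ITT population". This limits the consequence to the planned differences and their intervals.

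**Conclusion.** The point holds. SAP 10.3 as written omits two of the three safety contrasts that the Protocol requires, no other SAP safety section supplies them, and Section 12 declares no change. The conclusion rests on reading the repeated phrase the same way in both clauses of one sentence. The probable cause is a drafting slip.

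The effect is limited to planned safety output. The primary test, alpha, sample size and efficacy analyses are untouched.

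A reader might infer more, and the documents do not support it:

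- **That the sponsor chose to drop the dose-specific comparisons.** No rationale is given, and the sentence otherwise follows the Protocol's structure.
- **That dose-specific safety data would be unavailable.** Results by arm remain in the tables.
- **That the Protocol promised these differences for every common TEAE.** It ties them to patients with at least one related TEAE, SAE or AESI. The 2% list and the common TEAEs are the SAP's additions.
- **That pooling would hide a dose-specific excess.** Whether it would depends on event counts and exposure by arm. The documents do not give these, so no numerical size is claimed.

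**What to change.** In SAP 10.3, replace the contrast wording so that differences in exposure-adjusted event rates, with 95% confidence intervals, are given for SEL-212A vs placebo, SEL-212B vs placebo and combined SEL-212 vs placebo. State that they cover patients with at least one related TEAE, at least one SAE and at least one AESI, as in Protocol 13.5.2, in addition to the SAP's own list (SAEs and AESIs in at least 2% of individuals, and the most common TEAEs). If A vs B is also wanted, name it as an addition.

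If the present wording is intended, declare the departure from Protocol 13.5.2 in SAP Section 12.

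The cost is a sentence or two in the SAP and minor programming, with no new data and no change to the efficacy analyses. The change is best made before unblinding, so that there is no doubt which contrasts were pre-specified.
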